The TSST procedure is widely recognized as the gold standard for evoking stress response in the laboratory (Dickerson & Kemeny, 2004). It begins when the participant is told that (s)he will soon have to perform both a speech and arithmetic task in front of an audience. They are told that the topic of the speech is why (s)he should be hired for a particular job (the participant's "dream job"). The participant will deliver the speech as though speaking to a group of hiring managers. The experimenter then tells the participant that (s)he has 5 min to prepare the speech, and starts the countdown clock (placed in view of the participant). The experimenter leaves the room to allow the participant to prepare. Five minutes later, three individuals unfamiliar to the participant (the audience) enter the room and are seated; the participant is instructed by one audience member (the spokesperson) to stand and begin his/her prepared speech (without notes). The speech is delivered for 5 min; if the participant pauses, (s)he is instructed by the spokesperson to continue. At the end of the speech task, the participant is instructed to serially subtract 13 from 1,022 as quickly and accurately as possible. The mental math recitation continues for 5 min, and at its conclusion, the spokesperson instructs the participant to stop and be seated, and the audience leaves the room. The total time for the TSST procedure is approximately 15 min.

Laboratory Procedure Timeline

TIME	PROCEDURE(S)	MEASUREMENT(S)		
10-10:55 AM	General Assessment & Preparation	CO Assessment; Breathalyzer; UDS; Saliva collection (if not done at home); NWSC; STAI, Mood Form; DDT.		
11:00-11:30 AM	Placement of HR & SC sensors & BP cuff; Baseline 1 Measurements; Snack.	CQ; CREMA Mood & Stress Assessment; NWSC; HR, SC & BP; Cortisol.		
12:00 Noon	Intranasal Administration of Oxytocin or Placebo			
12:30 PM	Baseline 2 Measurements	CQ; CREMA Mood & Stress Assessment; NWSC; HR, SC & BP; Cortisol		
12:45-1:00 PM	Trier Social Stressor Task (TSST)			
1:00 PM	Immediate post-TSST assessment; SRT begins.	CQ; CREMA Mood & Stress Assessment; NWSC; HR, SC & BP; Cortisol; DDT		
1:20 PM	20-minute, post-TSST assessment	*Cortisol & subjective stress (verbal report) will be assessed 20, 40 & 60 min. post-TSST.	*CQ, CREMA Mood & Stress Assessment, NWSC, HR, SC & BP will be assessed when each participant ends SRT and during ASP at 30 and 60 min.	
1:40 PM	40-minute, post-TSST assessment			

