1:50 PM	Maximum duration of SRT reached. Latest time that ASP begins.			
2:00 PM	60-minute, post-TSST assessment			
2:50 PM	ASP Ends.			
2:50-3:20 PM	Sensors removed; participant debriefing and compensation.			

Table Key: UDS=Urine Drug Screen; CO= Carbon Monoxide; NWSC=Nicotine Withdrawal Symptom Checklist; STAI=State-Trait Anxiety Inventory; DDT = Delay Discounting Task; CQ=Craving Questionnaire; CREMA=Cue Reactivity Ecological Momentary Assessment; HR=Heart Rate; SC=Skin Conductance; BP=Blood Pressure; SRT=Smoking Resistance Task; ASP=Ad libitum Smoking Period.

The participant will then complete the Smoking Resistance Task (SRT), which is a empirically validated laboratory model of smoking lapse behavior (McKee, 2009; McKee, Krishnan-Sarin, Shi, Mase, & O'Malley, 2006; McKee, et al., 2011). The task involves testing the ability of overnight abstinent smokers to resist smoking in a situation where they are free to smoke but continued abstinence is reinforced with money. In the present case, a participant's preferred brand of cigarettes and a lighter will be presented on a tray. The experimenter will explain that the participant may begin smoking at any time, but the participant will be eligible to earn \$1.50 for every 5 minutes the participant is able to "resist" smoking (up to a total of 50 minutes or \$15). Once (s)he elects to smoke, the participant will begin the Ad libitum Smoking Period (ASP), in which (s)he is permitted to smoke as much as desired over the next hour in the laboratory. Topographical features of smoking behavior will be measured using the CReSS Pocket (CReSS, Borgwaldt KC, Inc., Richmond, VA), a self-contained, battery-operated device. In addition, the experimenter will record the number of cigarettes smoked.

Oxytocin/Placebo Administration: As noted above, participants will be administered 40 IUs of oxytocin or matching placebo nasal spray at approximately 12:00 noon. This dose and timing of administration was selected based on previous studies that have used similar doses of oxytocin (Ditzen et al., 2009; Heinrichs, et al., 2003; Macdonald et al., 2011), as well as our own previous pilot work (see Preliminary Data). Intranasal oxytocin and matching placebo will be compounded by MUSC Investigational Drug Service (IDS). The concentration of oxytocin will be 40 IUs/ml. Randomization will be done by the MUSC Investigational Drug Service, who will keep a record of the blind and be available should unblinding be necessary.

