menses. Linear models may thus be inappropriate. Traditional analyses group the hormone curves based on the estimated phases of women's menstrual cycle (follicular and luteal) for the analyses. In addition to performing the data analyses using the same method, analysis will be extended to incorporate the non-linear patterns of an individual's hormone profile. This method will be based on a non-linear regression model that has two to three segments, each one of which may be either quadratic or linear (Marrie, Dawson, & Garland, 2009). The 'joint-points' at which the segments meet, which are referred to as knots, will also be treated as unknown and determined through the modeling process. After identifying the segments, regression models assessing hormone measures against the outcome (e.g., cue-elicited craving) in each segment will be assessed and the results interpreted accordingly.

Aim 2: Hypotheses 1 and 2 - To test for gender and medication (oxytocin versus placebo) effects on reactivity profiles to the TSST during the laboratory session, a linear mixed effects model in which the dependent variables of interest are craving, stress and neuroendocrine (cortisol) response, and the primary independent fixed effects are gender, treatment group, and a random subject effect will be utilized. To account for the repeated measures, a covariance pattern for the error structure (such as an AR(1)) will be considered. The primary goal of this analysis will be to determine if the response to TSST is significantly different between females and males and/or significantly different between those who received oxytocin versus placebo (main effects of gender and medication). Additionally, as a secondary analysis, the interaction between gender and medication condition will be explored.

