To test the hypothesis that females will have a shorter latency to return to smoking than males, a discrete analog to the Cox proportional hazards model will be used. A complementary log-log model for interval censored survival times will be employed (Allison, 1982; Prentice & Gloeckler, 1978) that will take into account the interval nature of the time frame within which the return to smoking occurs. Also considered will be standard Cox proportional hazards models to compare time to begin smoking. Puff intensity, flow rate, and number of puffs will be assessed using a topography device as participants smoke freely for 1 hour following the smoking resistance task. Longitudinal data analytic methods will be applied to the craving, stress and cortisol data obtained during the laboratory session for all time points before and after the TSST.

Hypothesis 3 - To test the association between the estrogen to progesterone ratio and laboratory stress reactivity in women, a linear model will be developed to assess the relationship between hormones and subsequent stress reactivity. The dependent variables of interest will be the craving, stress and neuroendocrine (cortisol) response to the TSST while the independent variables will include the change in the hormone ratio over the week preceding the lab visit as well as the hormone ratio on the day of the visit. Assumptions such as linearity of the relationship between the hormones and reactivity measures, homoscedasticity, and normality of the error distribution will be assessed and variables will be transformed as necessary.

C3k. Operational Plan and Research Timetable.

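### Aim 2 analyses the response to the TSST over all time points, but only the 1:00 PM post-stressor value is always taken before smoking access, so smoking effects enter the gender and oxytocin contrasts.

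*Combined protocol and SAP*

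**What the plan says.** **Analysis (C3j, Aim 2, Hypotheses 1 and 2).** A linear mixed model is planned for craving, stress and cortisol: "the primary independent fixed effects are gender, treatment group, and a random subject effect will be utilized". Its goal is to "determine if the response to TSST is significantly different between females and males", and likewise between oxytocin and placebo, both framed as main effects. The next paragraph applies longitudinal methods to these outcomes as "obtained during the laboratory session for all time points before and after the TSST". No time term, primary time point or smoking phase is named.

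**Schedule (C3f, Laboratory Procedure Timeline).** The 1:00 PM row reads "Immediate post-TSST assessment; SRT begins", and craving, mood/stress and cortisol are all measured there. After that:
- "Cortisol & subjective stress (verbal report) will be assessed 20, 40 & 60 min. post-TSST".
- Craving and the CREMA mood/stress scale "will be assessed when each participant ends SRT and during ASP at 30 and 60 min", where ASP is the ad libitum smoking period.
- At 1:50 PM: "Maximum duration of SRT reached. Latest time that ASP begins".

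The SRT description in C3f says that "the participant may begin smoking at any time". Choosing to smoke ends the SRT and starts the ASP.

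**Expected differences in smoking.** Aim 2 Hypothesis 1 predicts a shorter latency to smoke in women. C1 (Relevant Oxytocin Experience) proposes to examine whether oxytocin increases resistance to smoking.

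**The concern.** The stated target is the reaction to a stressor that ends at 1:00 PM. From that moment 12-hour-abstinent smokers may smoke when they wish, and most later measurements are taken at or after that choice. A cortisol sample at 20 or 40 minutes follows smoking in an early lapser and precedes it in a resister. The later craving ratings are tied to the end of the SRT and to the ASP.

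If one group smokes sooner, pooled values reflect both how that group reacted to the TSST and when it smoked. For gender, a difference in stress response is confounded with a difference in smoking timing. For oxytocin, smoking is a possible path from drug to outcome, so the contrast answers a broader question than the one posed. The protocol treats smoking as able to change craving: the mCEQ, given after a cigarette in the ASP, has a craving-relief subscale (C3g).

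**Working it through.** **Step 1. The plan's own power figure.** C3i gives 144 completers, d = 0.50, type I error 0.05 and 80% power for the TSST contrasts. The 96:48 gender split and two-sided testing are stated there for the CREMA calculation. C3a gives equal probability of drug or placebo, hence 72:72. With one value per participant and a normal approximation, power = Φ(d / √(1/n₁ + 1/n₂) − 1.96).
- Gender: √(1/96 + 1/48) = 0.1768; 0.50/0.1768 = 2.828; Φ(0.868) = 80.7%.
- Drug: √(2/72) = 0.1667; 0.50/0.1667 = 3.000; Φ(1.040) = 85.1%.

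The stated 80% is therefore met with a single post-TSST value per participant.

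**Step 2. Which values precede smoking.** Let L be the minutes from 1:00 PM to the end of the SRT, from 0 to 50. Craving is rated at 0, L, L+30 and L+60. Cortisol is sampled at 0, 20, 40 and 60. Stress has seven values: the CREMA scale on the craving schedule, plus verbal reports at 20, 40 and 60. The value at 0 is read as taken before the SRT opens, following the order in the timeline row. Values at or after the end of the SRT:

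| L (min) | Craving | Stress | Cortisol | All |
|---|---|---|---|---|
| up to 20 | 3 of 4 | 6 of 7 | 3 of 4 | 12 of 15 |
| over 20 to 40 | 3 of 4 | 5 of 7 | 2 of 4 | 10 of 15 |
| over 40 to 50 | 3 of 4 | 4 of 7 | 1 of 4 | 8 of 15 |

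The rating at L marks the decision to smoke or the 50-minute cap, and probably precedes the first puff. Counting only values strictly after L, craving has 2 of 4, and the total runs from 10 of 15 (L under 20) down to 6 of 15 (L of 40 or more).

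**Step 3. Time since the stressor.** The two ASP craving ratings fall L+30 = 30 to 80 minutes and L+60 = 60 to 110 minutes after the TSST. They are aligned on time since the SRT ended, not on time since the stressor.

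**Step 4. What pooling could do (illustration).** Take the mean of the four post-TSST craving ratings, with a between-rating correlation of 0.70. That value is assumed, borrowed from the CREMA calculation in C3i. The variance is 0.70 + 0.30/4 = 0.775, so the SD is 0.880. Suppose the true effect is 0.50 in the first two ratings and 0.50·f in the two ASP ratings. The average d is then 0.50(2 + 2f)/4.

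| f (assumed) | Average d | Power, gender | Power, drug |
|---|---|---|---|
| 1 (unchanged) | 0.50 | 89% | 93% |
| 0.5 (halved) | 0.375 | 67% | 72% |
| 0 (absent) | 0.25 | 36% | 40% |

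For the halved case:
- Gender: 0.375/(0.880 × 0.1768) = 2.41; Φ(0.45) = 67%.
- Drug: 0.375/(0.880 × 0.1667) = 2.56; Φ(0.60) = 72%.

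With correlations from 0.5 to 0.9, the halved case gives 60–77% for gender and 65–81% for drug.

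**The case against.** **A longitudinal model may already contain time.** The plan speaks of reactivity profiles and longitudinal methods, so a time term is unstated rather than excluded, and such a model could yield the 1:00 PM contrast. This stands in part: the fault is under-specification. But the stated goal is main effects. A time term alone also does not separate participants who have smoked from those who have not at the same nominal minute.

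**The oxytocin contrast is randomised.** A reader might infer that it is biased. The documents do not support that. Comparing randomised arms remains valid for the total effect of the drug, including any effect through smoking; what is lost is a contrast specific to the TSST response. Nor does the plan predict that oxytocin delays smoking: C1 proposes to examine it, and Aim 2 Hypothesis 2 does not mention smoking behaviour.

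**Craving is rated at matched phases.** A reader might estimate a bias from the gap between women and men who have smoked by a given clock time. That does not fit craving, because the later ratings follow each participant's own end of SRT. Differences in time since the stressor and in amount smoked remain possible, but the documents give nothing from which to size them.

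**The direction is not always against the hypotheses.** A reader might infer that smoking always hides the predicted effects. For cortisol this fails: Hypothesis 1 predicts less reactivity in women, and the documents give no sign for the effect of smoking on cortisol. The distortion could run either way.

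**Cortisol is not mostly post-smoking by design.** Three of four samples are affected only when the SRT ends by 20 minutes, and no latency distribution is given. Some who reach the cap may smoke later in the ASP or not at all.

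**Conclusion.** The point holds as a gap in the Aim 2 analysis plan that should be fixed. One post-TSST assessment, at 1:00 PM, is always before smoking access. Two of four craving ratings lie in the smoking period and a third is tied to the decision to smoke. One to three of four cortisol samples fall at or after the end of the SRT. Analysing all of them as response to the TSST confounds the gender contrast and makes the oxytocin contrast a total effect.

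The size is unknown, and for cortisol so is the direction. The fall to 67% and 72% power rests on the assumed correlation and on an assumed halving of the effect. If smoking left the effect unchanged, pooling would raise power. The hypothesis on which C3i powers the study, the gender difference in cue reactivity under CREMA, is not touched, and the 1:00 PM data are collected in any case.

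**What to change.** In C3j, Aim 2, Hypotheses 1 and 2:

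1. **Craving and subjective stress.** Make the 1:00 PM value, completed before the SRT opens and adjusted for the pre-stressor baseline, the primary post-TSST outcome. State which baseline is meant: Baseline 1 precedes dosing, whereas Baseline 2 follows it and may already carry a drug effect. Report the end-of-SRT and ASP ratings separately as smoking-period outcomes.
2. **Cortisol.** Add time and group-by-time terms and report contrasts by time point. Exclude the 60-minute sample from the primary TSST contrast, since everyone is in the ASP by then. Interpret the 20- and 40-minute contrasts as total effects that include smoking. The later verbal stress reports can be shown the same way, as secondary.
3. **Sensitivity analyses only.** These may restrict to pre-smoking samples or adjust for time since first cigarette. Both select or condition on a choice made after randomisation, possibly driven by the outcome, and the plan should say so. SRT latency is censored at 50 minutes, so for participants who reach the cap the time of first cigarette needs another source.

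The cost is plan wording, settled before unblinding, with no new visits or samples for the primary analysis. The primary craving and stress contrast uses fewer values, but one value per participant still gives 80.7% (gender) and 85.1% (drug) at d = 0.50, before any gain from baseline adjustment.

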Following the two weeks of CREMA data collection, a laboratory session will be conducted to investigate responses to acute dosing of oxytocin (versus placebo) in context of controlled evaluation of stress reactivity and smoking behavior. Prior to the session, participants will abstain from smoking for 12 hours and provide a salivary sample for measurement of stress and sex hormone (cortisol, estradiol, progesterone, and testosterone) levels. Participants will receive a double blind intranasal dose of oxytocin or placebo and will then be exposed to the Trier Social Stress Test (TSST). Measures collected at multiple time points during the laboratory session will include subjective craving, stress, and negative emotion as well as heart rate, blood pressure, skin conductance, and cortisol. Immediately following the TSST, participants will complete a smoking resistance task (SRT) in which they will receive a monetary reward for every 5-min period they can resist smoking. After completing the SRT, participants will be allowed to smoke freely during a one-hour ad libitum smoking period (ASP), with smoking topography assessed via a portable device.

Aim 1: Evaluate gender and sex hormone influences on reactivity to stressful and smoking-related cues presented, via CREMA, in the natural environment of smokers.

Hypothesis 1: Female smokers will be more reactive (craving ratings) than male smokers to stressful and smoking-related cues presented in the natural environment.

Hypothesis 2: Among female smokers, estrogen to progesterone ratio will be positively related to reactivity (craving ratings) to stressful and smoking-related cues presented in the natural environment.

Aim 2: Evaluate gender, sex hormone, and oxytocin administration influences on stress, craving, and smoking behavior response to a laboratory-based stressor task (TSST).

Hypothesis 1: Female smokers will evidence greater subjective stress, craving, and smoking behavior (e.g., shorter latency to smoke during the SRT and greater number of puffs during the ASP), but less neuroendocrine reactivity (cortisol), to the TSST than male smokers.

Hypothesis 2: Oxytocin, relative to placebo, will attenuate subjective stress, craving, and neuroendocrine responses to the TSST.

Hypothesis 3: Among female smokers, estrogen to progesterone ratio will be positively related to craving reactivity during the TSST.

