Relevant Oxytocin Experience. Members of MUSC’s SCOR research team ([name], [name]) recently completed a pilot study examining the effects of intranasal oxytocin vs. placebo on the subjective craving and anxiety responses of marijuana-dependent individuals before and after administration of the Trier Social Stressor Task (TSST). Figure 4 depicts the mean craving responses of the oxytocin vs. placebo treated groups prior to receiving oxytocin/placebo (Pre-Med BL), after receiving oxytocin/placebo but prior to the TSST (Post-Med BL) and immediately following the TSST (Post-TSST). The data indicate that while the groups exhibited similar levels of craving prior to medication administration, oxytocin appears to have a dampening effect on craving both before ($p = .06$) and after ($p = .03$) the TSST is administered. Parallel finding were observed for subjective anxiety (not shown). Thus, these preliminary findings suggest that oxytocin may have potential as therapeutic adjunct for managing both basal and stress-elicited craving and anxiety in substance dependent individuals. The proposed project will employ a similar research strategy with nicotine dependent smoker to examine whether oxytocin (vs. placebo) (a) reduces stress and craving reactivity to the TSST, and (b) enhances smoking resistance and attenuates smoking behavior/topography. Since the sex hormone levels of a substantial number of male and female smokers will be quantified in the two-week period preceding the laboratory stress procedures, the proposed research design will permit an exploratory analysis of the association between sex hormone levels and oxytocin’s impact on laboratory measures of stress reactivity/smoking behavior and also the interaction between medication condition and gender.

[figure not shown]
C2. Research Team

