All paper-based assessments will be entered into SPSS databases using dual data entry methods for 20% of cases. Semi-annual database management and data integrity audits will be conducted. Hormone and cortisol data will be obtained from MUSC's CTSC in pre-formatted data files. HR and SC data will be acquired via specialized software and hardware (Biopac Systems, Inc.) interfaced with a computer. Standardized file formats will facilitate the rapid determination of summary values to be used for analysis purposes. The CREMA data will be automatically uploaded to a server on a daily basis and will be stored in a standard file format (to be determined in collaboration with [name] (Founder of Slicker Interactive & CREMA software developer). All data will be de-identified using participant ID number.

Statistical Analysis

Univariate descriptive statistics and frequency distributions will be calculated for all variables. Departures from distributional assumptions for the proposed parametric methods will be identified and appropriate transformations of the data will be applied or alternative procedures (semi/non parametric methods) will be employed. Baseline values for demographic, clinical, and other prognostic variables will be compared for imbalance across gender and treatment groups. These analyses will identify potential confounding variables to be used as covariates in subsequent analysis.

Aim 1: Hypothesis 1 - To test the overall hypothesis that females will be more reactive than males to stressful and smoking-related cues presented in the natural environment, a linear mixed effects model will be employed. The dependent variable will be craving and the primary independent variable will be gender. In the modeling process, within-subjects factors of stimulus type (active and neutral cues) and presentation order will also be included.

Hypothesis 2 - To test the hypothesis that the estradiol to progesterone ratio will be positively related to cue-elicited craving in the natural environment, salivary hormone levels and craving in response to the CREMA picture cues will be assessed over 14 days. Hormone curves do not behave in a linear fashion, but may, in the example of progesterone, behave in a quadratic fashion preceding menses and a linear fashion following

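### The smoking-latency and Hypothesis 3 models do not name the randomised drug, and no test of oxytocin on smoking latency is specified

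*Combined protocol and SAP*

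**What the plan says.** - **Craving, stress and cortisol (C3j, Aim 2, Hypotheses 1 and 2).** A linear mixed model in which "the primary independent fixed effects are gender, treatment group, and a random subject effect will be utilized". This is the only Aim 2 model that names the drug.
- **Latency in the smoking resistance task (C3j, same block).** "To test the hypothesis that females will have a shorter latency to return to smoking than males, a discrete analog to the Cox" regression, fitted as a complementary log-log model for grouped times, with a standard Cox model also considered. No treatment term is named.
- **H3.** The Specific Aims state it as "Among female smokers, estrogen to progesterone ratio will be positively related to craving reactivity during the TSST". C3j proposes a linear model in which "the independent variables will include the change in the hormone ratio over the week preceding the lab visit as well as the hormone ratio" at that visit. No treatment term is named. The plan does not say whether the level, the change or both decide the hypothesis.
- **Covariates (C3j).** Baseline variables are compared across gender and treatment groups. "These analyses will identify potential confounding variables to be used as covariates in subsequent analysis".
- **Purpose.** Aim 2 covers the influence of oxytocin on smoking behaviour as well as on stress and craving. Section C1 says the project will examine whether oxytocin "enhances smoking resistance and attenuates smoking behavior/topography".
- **Timing and allocation.** The C3f timeline puts dosing at noon, the stress test at 12:45 and the resistance task from 1:00 PM. C3a gives oxytocin to about half of each gender.

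**The concern.** Both outcomes are measured after a randomised intervention that the protocol expects to change them. A model that follows the text leaves that factor out, so its variation goes into the residual. The latency analysis would then yield a gender contrast and no oxytocin contrast. If the drug comparison on resistance to smoking is wanted later, it would have to be specified after the fact.

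H3 raises a second question. A change score that ends on the lab day contains the lab-day ratio, so the two predictors are correlated by construction. Without a named test, it is unclear which coefficient answers a hypothesis that speaks only of the ratio.

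**Working it through.** **1. The plan's own figure.** Section C3i claims 80% power at d = 0.50 with 144 completers (96 women, 48 men), and a two-sided 0.05 level is stated for the main calculation. The standard error in SD units is sqrt(1/96 + 1/48) = 0.177. Then 0.50/0.177 = 2.83, 2.83 − 1.96 = 0.87, and power is 81%. The figure reproduces. For oxytocin versus placebo at 72 per arm, 0.50/sqrt(2/72) = 3.00 and power is 85%. C3i gives no effect size for H3 or latency, so the steps below rest on stated assumptions.

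**2. Leaving the drug out of H3.** With 1:1 allocation, an omitted drug effect of d SDs multiplies the residual variance by 1 + d²/4. Take a hormone effect that has 80% power with the drug in the model, so its expected z is 1.96 + 0.84 = 2.80.

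| Assumed d | Variance × | SE × | Power without drug |
|---|---|---|---|
| 0.3 | 1.0225 | 1.011 | 79.1% |
| 0.5 | 1.0625 | 1.031 | 77.6% |
| 0.7 | 1.1225 | 1.060 | 75.3% |

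**3. Leaving the drug out of the latency model.** This was simulated with 600 trials per scenario: 96 women and 48 men, half of each on oxytocin, and ten 5-minute intervals (the 50-minute task). Assumptions: gender hazard ratio 1.7 and baseline hazard 0.10 per interval. Both complementary log-log models were fitted to the same simulated data.

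| Assumed drug HR | Gender HR, without / with drug | Power, without / with drug |
|---|---|---|
| 0.8 | 1.71 / 1.72 | 67.0% / 68.3% |
| 0.67 | 1.70 / 1.73 | 66.3% / 69.5% |
| 0.5 | 1.65 / 1.69 | 57.0% / 60.7% |

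With no gender effect (baseline hazard 0.15), rejection rates without the drug were 4.5% (drug HR 0.67) and 4.3% (drug HR 0.5). With the drug they were 4.7% and 6.7%. Simulation error on a 5% rate is about 1.96 × sqrt(0.05 × 0.95/600) = 1.7 points, so these runs show no inflation from leaving the drug out. Simulation error on each power figure is about 4 points.

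**4. Level and change together in H3.** Let L be the lab-day ratio, W the ratio a week earlier, and rho their correlation. Assume equal variances and change D = L − W.
- corr(L, D) = sqrt((1 − rho)/2), so the variance inflation for L is 2/(1 + rho) and its SE is multiplied by sqrt(2/(1 + rho)).
- If reactivity is aL + bW, then aL + b(L − D) = (a + b)L − bD. The level coefficient is a + b, and the change coefficient is −b.

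The documents do not give rho. For an effect with 80% power when the level stands alone (r of about 0.28 with 96 women):

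| Assumed rho | SE × | Power of level coefficient |
|---|---|---|
| 0.7 | 1.08 | 73% |
| 0.5 | 1.15 | 68% |
| 0.31 | 1.24 | 62% |
| 0 | 1.41 | 51% |
| −0.19 | 1.57 | 43% |

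The values 0.31 and −0.19 are cos(2π·7/35) and cos(2π·7/25). They would apply if the ratio followed a pure sinusoid over the eligible 25 to 35 day cycle. Stable differences between women raise rho and shrink the cost.

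If change were instead a slope over eight daily samples with no day-to-day correlation, its correlation with the last day is 3.5/sqrt(42) = 0.54. The inflation is then 1/(1 − 0.54²) = 1.41, the SE factor 1.19 and power about 65%.

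**The case against.** The H3 predictor list is open, because it says what the model will include and not what it is limited to. The latency paragraph also sits in a block that opens with gender and medication effects. This is under-specification, not a stated exclusion. That stands, but nothing else in C3j brings treatment in: the covariate rule concerns baseline variables, and the latency hypothesis is framed by gender alone.

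Hypothesis 2 limits the oxytocin prediction to stress, craving and neuroendocrine response, so latency is hypothesised only for gender. That is correct. Aim 2 and section C1 nevertheless pose the drug question for smoking behaviour and resistance, and it has no analysis.

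A reader might infer that omitting the drug confounds the gender and hormone estimates. The documents do not support this. Allocation is about half and half within each gender, and random assignment is independent of hormone level in expectation. Chance imbalance is already reflected in the standard error.

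A reader might also infer that H3 is cut from 80% to 51% power. That needs a weekly correlation of zero, a simple difference as the change score, and the level coefficient as the deciding test. The plan states none of these. A joint test of level and change is unaffected by their correlation. Entering both also has a purpose: section C1 asks whether hormone effects are static or dynamic, and if change has its own effect, including it can reduce residual variance.

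**Conclusion.** The point holds as a modest gap in specification. As written, neither model contains the randomised factor, and C3j has no pre-specified analysis of oxytocin on smoking latency. The missing analysis matters more than the lost precision. At an assumed d = 0.5 the H3 standard error is about 3% larger than it need be. For latency the loss is roughly 3 to 4 power points, with slight attenuation of the gender hazard ratio, at assumed drug hazard ratios of 0.67 and 0.5; it is smaller at 0.8. The documents give no drug effect size for latency, so they do not establish that the drug is a strong covariate there.

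The H3 predictors are a secondary point: the deciding test is not named. The inflation from entering level and change together concerns the standard error of one coefficient, not type I error. Its size depends on a correlation and a definition of change that the documents do not give.

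**What to change.** Amend the Aim 2 text of C3j before unblinding:

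- **Latency.** Fit gender + treatment in the complementary log-log model, with gender × treatment as secondary. Report the oxytocin hazard ratio with its confidence interval from the same model.
- **H3 craving model.** Add treatment and Baseline 1 craving. Baseline 1 is taken before dosing; Baseline 2 is not.
- **H3 test.** Define the change score and name the deciding test. Either test the lab-day ratio alone as primary, with change in a secondary model, or use a joint two-degree-of-freedom test of level and change. The first is the more direct answer to the hypothesis as stated. The second keeps the static and dynamic questions together and spends one more degree of freedom.

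The cost is wording, one degree of freedom for treatment in each model and one for baseline craving in H3. No new data are needed.
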